2.3.3 Chimeric MOv18 IgG

A single IV infusion of increasing doses of chimeric MOv18 IgG was evaluated in 15 ovarian carcinoma patients (Molthoff et al., 1997). Administration of chimeric MOv18 IgG was described as uneventful with no significant changes in haematological, biochemical, or urine profiles noted at any time following injection. At doses of 50 mg or more, however, all patients experienced infusion-associated side effects such as fever, headache, and nausea/vomiting (Grade 1-2 on the World Health Organization Toxicity Scale). In a subsequent study, five ovarian cancer patients received weekly IV injections (50 mg) for 4 weeks (van Zanten-Przybysz et al., 2002). Administration was described as well tolerated and uneventful in all patients, although infusion-associated Grade 1 nausea, vomiting, headache, chills, flu-like symptoms, arthralgia and myalgia were reported. Three patients achieved stable disease for up to 4 months, 9 months and 14 months, respectively. Immunological effects of treatment were evaluated in this study but only minor changes were noted (increased antibody-dependent cell-mediated cytotoxicity [ADCC] associated with an increase in CD4+ and CD8+ fractions).

The use of radiolabelled MOv18 IgG1 as a radiotherapeutic agent has also been evaluated. In 24 patients with ovarian cancer the distribution of 1 mg of iodine radiolabelled MOv18 IgG was compared with that of the labelled IgG F(ab')2 fragments (Buist et al., 1993). In a separate study, iodine-131 radiolabelled MOv18 IgG1 was administered to eight patients intraperitoneally at doses of equivalent to 15, 20, 50 or 80 mg or intravenously to four patients at doses of 30, 50 or 75 mg (Buijs et al., 1998). Three patients with ovarian cancer were also administered 10 mg of iodine-131 radiolabelled chimeric MOv18 IgG (van Zanten-Przybysz et al., 2000). The dosimetry of iodine radiolabelled MOv18 IgG1 administered via the IP or IV route has also been examined. Fifteen patients with recurrent epithelial ovarian cancer received a total of 2 to 3 mg of iodine radiolabelled MOv18 IgG1 by a mixture of IP and IV injections (van Zanten-Przybysz et al., 2001). No toxicity attributable to FR α targeting was reported in any of these studies.

No human anti-chimeric antibodies were detected in these studies.

2.3.4 Farletuzumab

Farletuzumab (MORAb-003), a humanised IgG antibody directed against the FR has been evaluated in the phase III setting. In a phase I study in platinum-resistant epithelial ovarian carcinoma, farletuzumab was well tolerated at doses ranging from 12 mg/m² to 40 mg/m² (Konner et al., 2010). No treatment-

related serious adverse events (SAEs) occurred and no dose-limiting toxicity (DLT) was encountered. The most common treatment-related adverse events were hypersensitivity reactions (15 patients; 60%), fatigue (12 patients; 48%), and diarrhoea (4 patients; 16%). There were no clinically significant changes in cardiac, pulmonary or renal function and no evidence of human anti-human antibody formation. The most common hypersensitivity reactions were pyrexia and chills, which were mostly Grade 1 in severity and occurred during the first infusion. Pharmacokinetic analysis demonstrated a half-life of 5-11 days, consistent with other humanized monoclonal IgG antibodies (this finding was supported by a subsequent population PK analysis (Farrell et al., 2012). Anti-tumour activity was also seen, with four patients achieving a response according to CA125 tumour markers, and seven patients achieving stable disease on imaging. There were no objective responses but nine patients (36%) had stable disease and four patients had a CA125 reduction.

Preliminary data have been published from a phase II study of farletuzumab, conducted in patients with platinum-sensitive epithelial ovarian cancer after an initial remission period of 6-18 months (Armstrong et al., 2008). Twenty-eight asymptomatic patients were given single agent farletuzumab at a dose of 100 mg/m² until progressive disease occurred. After nine weeks of treatment, one patient showed a measured reduction in CA125 tumour marker by >75% and a further patient by >25%. Eight patients had stable disease and five patients remained on study for 15-25 weeks. Patients with symptomatic relapse were given standard chemotherapy with carboplatin and paclitaxel combined with farletuzumab. In total, results from forty-one patients were evaluated and amongst these patients, CA125 resolved to normal levels in thirty-seven patients. Six patients remained in remission for longer than their first remission. Although independent radiological reviews were not complete, a 70% response rate was seen. The drug combination was well tolerated, although with infrequent mild infusion reactions noted. Grade 3 toxicity was reported for single agent treatment (headache and abdominal disease secondary to progressive disease), and for farletuzumab in combination with chemotherapy (diarrhoea and neutropenia).

In December 2011, in a company press release, Morphotek, a subsidiary of Eisai Inc., announced the termination of FAR122 (NIH Clinical Trials identifier NCT00738699), a Phase III study of farletuzumab in platinum-resistant ovarian cancer. This decision was based on the results of an interim analysis indicating the study was unlikely to meet its statistically defined endpoints of progression-free survival and overall survival. Safety issues did not play a part in this decision. In January 2013, the company announced that a second phase III trial of farletuzumab (NCT00849667), in platinum-sensitive ovarian cancer, had failed to achieve its primary objective (improved progression-free survival). Overall, these phase I/II/III data suggest that farletuzumab has, at best, modest efficacy in patients with ovarian cancer. However, farletuzumab is well tolerated and adverse effects reported to date do not appear to be related to targeting of the FR in normal tissues.

2.3.5 Other approaches

Other therapeutic approaches targeting the FR include folate-targeted liposomes e.g. (Watanabe et al., 2012), folate-targeted nanoparticles and other novel delivery methods e.g. (Wang et al., 2012), bispecific antibodies (Canevari et al., 1995; Luiten et al., 1997), immunoconjugates of single chain antibodies (Melani et al., 1998), adoptive T-cell therapy using genetically modified T-cells expressing a chimeric anti-FR single-chain antibody (Kershaw et al., 2006), and dendritic cell vaccines transfected with mRNA encoding FR (Hernando et al., 2007).

Vintafolide, a conjugate of folic acid (the ligand for FR) and a vinca alkaloid is in clinical development for ovarian, lung and triple-negative breast cancer. In a phase I study, constipation, nausea, fatigue, and vomiting were the most commonly reported adverse events and constipation was dose-limiting (Lorusso et al., 2012). One partial response to therapy was observed in a patient with metastatic ovarian cancer. A subsequent randomised phase II study of vintafolide in combination with pegylated liposomal doxorubicin (the PRECEDENT study) showed a significant improvement in progression-free survival in patients with platinum-resistant ovarian cancer (Naumann et al., 2010) and this was the basis of an initial EU recommendation for conditional approval. However, an interim analysis of a confirmatory Phase III trial in platinum-resistant ovarian cancer (NIH Clinical Trials identifier NCT01170650; PROCEED trial) was negative and the application for conditional approval was withdrawn. However, evidence of anti-tumour activity has also been reported in a randomised phase II trial of vintafolide in FR-positive adenocarcinoma of the lung (Edelman et al., 2012). Importantly, in relation to the MOv18

IgE CRUKD/14/001 study, the adverse events reported to date for vintafolide do not suggest that toxicities are due to targeting of FR in normal tissues (consistent with clinical data for MOv18 IgG and farletuzumab).

For additional information concerning MOv18 IgE, refer to the Investigator's Brochure.

2.4 Rationale for the clinical study

2.4.1 Rationale for using IgE therapeutically

Monoclonal antibodies directed against tumour antigens have become an important treatment modality in the clinical management of both haematological and solid malignancies in the last 25 years. Several antibodies are now licensed and these humanised or chimeric antibodies behave in a manner similar to naturally occurring immunoglobulins (Reichert et al., 2007). All therapeutic antibodies licensed to date have been IgG antibodies (mainly IgG1). Although they have been shown to be efficacious in the clinical management of some cancers it is possible that other antibody classes - namely IgE - may have superior anti-tumour efficacy because of differences in tissue retention, higher receptor affinity, natural tissue surveillance activities, as well as activation and recruitment of a different spectrum of immune effector and inflammatory cells to the tumour site.

IgE antibodies are primarily known for their role in the immediate hypersensitivity reactions – the basis of conditions such as allergic rhinitis and asthma. IgE antibodies against allergens remain permanently bound to IgE receptors on the surface of IgE receptor-expressing cells such as mast cells, basophils and Langerhans cells. The cross-linking of Fc ϵ RI on mast cells by allergen, leads to the release of histamine and cytokines which increases circulation to the tissue and the influx and activation of inflammatory and potentially cytotoxic cells at the site of allergen provocation. These activated cells may also migrate to local lymph nodes to stimulate T cells which in turn migrate to the tissue (Gould et al., 2003). Overall, nonclinical data suggest that the efficacy of immunotherapy for solid tumours may be improved by the use of IgE antibodies in place of the conventional IgG. Nonclinical data and ex vivo data using clinical samples also indicate that MOv18 IgE will not trigger anaphylaxis when administered intravenously to humans, regardless of the presence of FR α -expressing tumours, circulating FR α or FR α -expressing cells.

2.4.2 Rationale for folate receptor alpha as a target

MOv18 IgE is a chimeric antibody raised against an epitope of the human FR α . The significance of this receptor as a tumour marker was discovered in 1991 when amino acid sequence analysis of a protein enriched on the surface of a human ovarian carcinoma cell line showed it to be FR α (Coney et al., 1991). Monoclonal antibodies that recognise FR α revealed that it was expressed on the majority of non-mucinous ovarian carcinomas. However, little to no reactivity was detected on non-epithelial tumours and normal tissues (Miotti et al., 1987). Subsequent publications have reported elevated FR α expression in up to 100% of ovarian carcinomas and lower but elevated expression levels in subsets of other cancers, including endometrial, kidney, lung, mesothelioma, breast, brain, and myeloid leukaemia (Franklin et al., 1994; Garin-Chesa et al., 1993; Holm et al., 1995; Holm et al., 1997; Holm et al., 1994; Parker et al., 2005; Ross et al., 1994; Weitman et al., 1992). Using the immunohistochemical technique planned for this study FR α overexpression is expected to be detectable in around 30-40% of ovarian and endometrial cancers, with less frequent expression in other tumour types (Lawson et al., 2010). The presence of elevated circulating concentrations of FR α has additionally been correlated with biologically more aggressive ovarian cancers (O'Shannessy et al., 2013; Toffoli et al., 1998).

A few normal tissues have been found to express FR α , although most express the protein at lower levels than that detected in FR α -positive carcinomas. Significant FR α expression has been reported in the proximal tubules of the kidney (luminal surface), the choroid plexus, intestinal brush-border membranes, type 1 and type 2 pneumocytes of the lung and placental tissue (Antony et al., 1981; Birn et al., 1997; Birn et al., 1993; Holm et al., 1991; Morshed et al., 1997; Zimmerman, 1990). Expression of FR α in these tissues is generally not accessible to circulating antibodies and so FR α is effectively a tumour-specific antigen.

CONFIDENTIAL

In clinical trials to date, FR α has been targeted with IgG antibodies. These antibodies have been well tolerated with no evidence of toxicity secondary to FR α binding in normal tissues. However, anti-tumour efficacy has been disappointing. [REDACTED]

[REDACTED]

[REDACTED]

This study will be a proof of principle study, primarily demonstrating the safety of an alternative antibody class in cancer immunotherapy.

3 STUDY DESIGN

3.1 Study objectives and endpoints

Primary Objectives	Endpoints
To assess the safety and tolerability of MOv18 IgE	
 • AEs and DLTs • Dose-independent significant toxicity (Section 3.3.2) • SAEs • Laboratory parameters 
AEs, SAEs and laboratory abnormalities will be graded according to NCI-CTCAE Version 4.02.
 
Causality of AEs/SAEs will be assessed by the investigator. Infusion-related events will be categorised as due to IgE-mediated mast cell degranulation (anaphylaxis) or cytokine release syndrome.

Secondary Objectives	Endpoints
To determine a recommended dose for Phase II evaluation	The recommended phase II dose (RP2D) will be based on safety data (the Maximum Tolerated Dose [MTD]; see definition in Section 3.4), and/or efficacy data (the dose at which evidence of anti-tumour activity is seen), and/or pharmacodynamic data, or will be the maximum evaluated dose (50 mg).
To document possible anti-tumour activity in patients treated at doses likely to be pharmacologically active	
Best response (according to RECIST 1.1) in patients receiving at least one dose of MOv18 IgE
 
CA125 response in patients with elevated CA125 at baseline

To describe the pharmacokinetics of MOv18 IgE	Serum concentrations of MOv18 IgE
Tertiary Objectives	Endpoints
[REDACTED]	[REDACTED]

3.2 Design of the Study

This is a multi-centre, first in human, Phase I, open label, dose escalation study. Approximately 25 evaluable patients with advanced, unresectable solid tumours expressing the FR α will be entered into this study. The final number will depend on: the number of dose escalations required to reach DLT, or

to reach a threshold frequency of dose-independent significant toxicity (Section 3.3.2) or to reach the maximum planned dose level (50 mg).

It is expected that the study will take about 4 to 5 years depending upon the number of cohorts explored during dose escalation.

MOv18 IgE will be administered as an IV infusion. Patients in all cohorts will receive a total of six doses of MOv18 IgE at 1-week intervals (over an initial dosing period of 6 weeks). This dosing period, called the 'Initial Treatment Period', is considered a loading phase. During this period, three weeks of treatment is considered one cycle.

Should additional drug supply become available during the study (for example if dose escalation does not proceed through all the planned dose levels), patients in any cohort who appear to be benefitting from MOv18 IgE may be given up to three further doses of MOv18 IgE at fortnightly intervals, starting two weeks after the sixth dose of MOv18 IgE, and continuing at the same dose level as the last dose received. This additional period is considered a maintenance phase. The total number of doses for patients completing the 'Initial Treatment Period' and the 'Maintenance Period' would be 9 over a treatment period of 12 weeks.

Please refer to Figure 3: MOv18 IgE Dosing Schedule in Section 5.3.

It is planned that all patients will receive a flat dose of MOv18 IgE, without adjustment for body weight or surface area. The starting dose will be 70 µg and dose escalation will be carried out through defined dose levels up to a maximum dose of 50 mg (see Section 5.4 Dose Escalation Scheme). However, a switch to weight-based dosing and/or intra-patient escalation will be considered during the course of the trial, if emerging clinical data suggest that this could be beneficial, for example by reducing any large inter-patient variations in PK.

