3.5 Patient evaluability

All patients who receive any amount of MOv18 IgE, either by IV infusion or as a skin prick test, will be evaluable for safety. However, dose escalation decisions require at least one or three patients (depending on the cohort) to receive 3 doses of IV MOv18 IgE without DLT (see [Section 5.4](#)).

All eligible patients who receive at least one dose of IV MOv18 IgE and have a baseline and at least one post-baseline disease assessment will be evaluable for response according to RECIST version 1.1 (see Appendix 3). For this study, to be assigned a status of complete response (CR) or partial response (PR), changes in tumour measurements do not need to be confirmed by repeat measurements four weeks later. To be assigned a status of stable disease (SD), follow-up measurements must have met the SD criteria at least once and at least six weeks after the initial dose of MOv18 IgE is given.

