5.4 Dose escalation scheme

The planned dose escalation scheme is summarised in Table 1. Additional cohorts may be added to evaluate intermediate dose levels or to evaluate alternative dosing schedules, depending on emerging safety information and/or pharmacokinetic data if available. Non-clinical studies have indicated that efficacy in rat xenograft models occurs at 5 to 10 mg/kg. This equates to a surface-area scaled human dose of approximately 50 to 100 mg. However, the plasma half-life of IgE in rat is considerably shorter than in human (12 hours versus 2 days) (Hanashiro *et al.*, 2001, 2002). Efficacious doses in the rat were associated with plasma rMOv18 IgE levels sufficient to represent at least 50% of total plasma IgE

for several days after each dose. This is expected to result in a prolonged wave of rMOv18 IgE loaded effector cells entering tissues.

It was originally estimated that in humans a dose of 10 to 25 mg/patient would be required to produce a similar effect (dependent on the patient's endogenous IgE levels). A flat dose escalation scheme, and a possible intra-patient escalation scheme, is therefore proposed which rapidly ascends (using single-patient cohorts) to doses likely to compete with endogenous circulating IgE and then proceeds with more patients per cohort as endogenous IgE levels are exceeded.

Table 1: Planned dose escalation scheme (Flat Dosing)

Cohort	Dose level	Planned no. patients/cohort	Actual no. patients/cohort
1	70 µg	1	2
2	250 µg	1	8
3	500 µg	1	6
4	700 µg	1	3
5	1.5 mg	3	3
6	3 mg	3	3
7	6 mg	3	TBC
8	12 mg	3	TBC
9	25 mg	3	TBC
10	50 mg	3	TBC

As of October 2020, recruitment to Cohort 6 (3mg) has been completed and the trial protocol has been amended to allow intra-patient dose escalation (see Section 5.4.1)

Initially, patients were enrolled in cohorts of one patient (Cohorts 1-4; 70 – 700 µg doses of MOv18 IgE) as the planned doses were low (based on a conservative approach to safety) and were considered unlikely to provoke a significant biological response. In case of toxicity at these dose levels, an additional two to five patients could be added to better evaluate safety.

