For Cohorts 5-10 (flat dosing) (1.5 - 50 mg doses of MOv18 IgE), three patients will be enrolled per cohort, with an additional three patients added to a cohort if needed for toxicity, as outlined below (Table 2). No further dose escalation is planned after Cohort 10 (i.e. 50 mg will be the top dose evaluated). For Cohorts 7-9 (intra-patient escalation), a minimum of 1 patient will be enrolled per cohort (see 5.4.1).

If drug supply permits, one or more cohorts may be expanded up to six patients to further explore the safety and efficacy of MOv18 IgE.

One or more cohorts may be repeated but with administration of prophylactic medication (antihistamine, antipyretic and/or corticosteroid), if considered medically appropriate by the Trial Steering Group (see Section 3.6). Under these circumstances, the prophylactic medication should be given after the skin prick test (before IV administration of MOv18 IgE). Any prophylactic medication will be used within its marketing authorisation.

Before commencement of a new cohort, all patients treated at the previous dose level must have received at least three doses and completed at least three weeks since the first dose. For the second patient in any cohort, the first patient in that cohort must have received at least two doses and been followed for at least 24 hours after the last dose. The second, third and subsequent patients in a cohort (if needed) must not receive their first treatments on the same day. If a patient is withdrawn from the study prior to receiving three doses of study medication without experiencing a DLT or a positive skin prick test, a replacement patient will be added to that dose level.

Decisions on dose escalation will be based primarily on toxicities encountered after the first two doses of MOv18 IgE in each cohort (see Table 2), or the first two doses of cycle 2 for patients undergoing intra-patient dose escalation. However, if available, data on toxicities occurring after later doses will also be taken into consideration. The decision to start a new cohort, and selection of the MOv18 IgE dose for each cohort, will be agreed by investigators and sponsor on review of the toxicities experienced by the preceding cohort during the three-week period from first dosing of each patient. The availability of paired pre-treatment and on-treatment tumour biopsies will also be taken into consideration in decisions on starting a new cohort since paired tumour biopsies are required for all patients.

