**A minimum of 1 patient will be dosed in each cohort, the final number will be dependent on review of safety data from that dose level.

(i) indicates this is an intra-patient escalation cohort

Figure 4: Intra-patient dose escalation: Example of planned escalation

The TSG to review all data and pay careful consideration to the safety of any current or future patient before making any decisions. Planned escalation may vary from the below based on TSG review of emerging safety data.

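### Is the stated size of about 25 evaluable patients out of date, given that Table 1 already counts 25 patients by Cohort 6?

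*Protocol*

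**What the plan says.** Section 3.2, in the same terms as the synopsis, gives the size as "Approximately 25 evaluable patients with advanced, unresectable solid tumours". It then qualifies the figure: "The final number will depend on: the number of dose escalations required to reach DLT", or to reach a threshold frequency of anaphylaxis, or to reach the 50 mg top dose.

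Table 1 in Section 5.4 lists planned and actual patients by cohort. The actual numbers stop at Cohort 6 ("As of October 2020, recruitment to Cohort 6 (3mg) has been completed"), and Cohorts 7 to 10 are marked as still to be confirmed. The cohort sizes can grow:

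- For Cohorts 1 to 4, planned at one patient each, if toxicity occurs "an additional two to five patients could be added to better evaluate safety".
- For flat Cohorts 5 to 10, "three patients will be enrolled per cohort, with an additional three patients added to a cohort if needed for toxicity".
- For a patient withdrawn before three doses without a DLT or a positive skin prick test, "a replacement patient will be added to that dose level".
- For intra-patient Cohorts 7 to 9 (Table 3), "A minimum of 1 patient will be dosed in each cohort".

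The protocol has three kinds of evaluability. For safety, Section 3.5 says: "All patients who receive any amount of MOv18 IgE, either by IV infusion or as a skin prick test, will be evaluable for safety". For response, Section 3.5 asks for at least one IV dose plus a baseline and a later disease assessment. For dose review, Section 5.5.3 asks for more than 80% of three infusions unless the Trial Steering Group (TSG) agrees otherwise. The size statement names none of the three.

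**The concern.** A reader who wants to know how many people will be exposed in this first-in-human study looks at the synopsis and Section 3.2. The number there equals the number already entered at 3 mg or below, while Section 5.4 originally estimated that 10 to 25 mg per patient would be needed. Taken together, the two places suggest that Table 1 was updated as the study ran and the headline size was not. If so, the protocol would understate total exposure, and it would be unclear whether the stated size had been used up or was still some way off.

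**Working it through.** **Inputs.** Planned and actual cohort sizes from Table 1, intra-patient cohort sizes from Table 3, and expansion limits from Section 5.4. No power formula applies, because Section 13.1 makes the analysis descriptive.

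**1. Where 25 could come from.** The protocol gives no derivation. The planned column of Table 1 sums to 4 × 1 + 6 × 3 = 22. One three-patient expansion gives 22 + 3 = 25. This is one route that reproduces the figure, and it counts the patients needed for dose decisions. It is an inference.

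**2. Enrolment to Cohort 6.** Actual: 2 + 8 + 6 + 3 + 3 + 3 = 25. Planned: 4 × 1 + 2 × 3 = 10. The excess lies wholly in Cohorts 1 to 4, with 2 + 8 + 6 + 3 = 19 against 4 planned.

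**3. Safety reading.** Assume that all 25 received some MOv18 IgE.

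| Remaining cohorts | Total | Against 25 |
|---|---|---|
| Intra-patient 7 to 9, one patient each | 25 + 3 = 28 | +12% |
| The same, then a flat Cohort 10 of three | 25 + 6 = 31 | +24% |
| Flat 7 to 10, three each | 25 + 12 = 37 | +48% |
| Flat 7 to 10, all expanded to six | 25 + 24 = 49 | +96% |

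The second row is hypothetical: Table 3 ends at Cohort 9 and the protocol does not describe that sequence. Early stopping would lower these totals. Several routes would raise them: replacements, repeated or intermediate cohorts (Section 5.4), expansion of intra-patient cohorts (Section 5.4.1) and the three or more patients treated below the maximum administered dose (Section 5.4.2).

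**4. Dose-review reading.** How many of the 25 qualify is not stated. Assume between 10, the planned number for Cohorts 1 to 6, and all 25.

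- With three one-patient intra-patient cohorts: 10 + 3 = 13 to 25 + 3 = 28.
- With four flat cohorts of three: 10 + 12 = 22 to 25 + 12 = 37.

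Both ranges contain 25, so on this reading the stated size is neither confirmed nor contradicted.

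**5. What Cohort 2 shows.** It has 8 patients, whereas the toxicity rule for Cohorts 1 to 4 allows at most 1 + 5 = 6. Replacements would explain this. So would a cohort repeated with prophylactic medication (Section 5.4), or extra patients without predisposing factors agreed by the TSG (Section 5.4.2). The 8 therefore does not tell us how many patients are evaluable for dose review.

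**6. Does anything use the 25?** Table 2 works on DLT counts within a cohort. The anaphylaxis review in Section 3.4.2 takes in everyone who received the drug, whatever that number is. Section 13 starts the final analysis on early termination, or once all patients have had the opportunity for two cycles and have finished follow-up. Section 12 mentions a required number of patients, but only in describing a stop for toxicity before that number is reached; it does not make 25 a trigger.

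**The case for a change.** The best case for a change runs as follows. Both statements stand in the same current version, so this is not a difference from superseded text. The primary objective is safety, which makes the number exposed the natural total, and on that count any further cohort takes the study past 25. The caveat in Section 3.2 covers the course of escalation, yet the excess arose inside Cohorts 1 to 4 from added patients. And if the reader cannot tell which kind of evaluability is meant, the stated size says little.

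The additions stand, and so does the observation that the kind of evaluability is not named. The step to *out of date* does not. Under Section 3.5 even a skin prick test alone makes a patient evaluable for safety, so on that reading the word hardly restricts the count. In an escalation study with replacement and dose-review rules, it more naturally refers to patients who count towards dose decisions, and the planned column of Table 1 fits that reading without proving it. The link between the 25 and the safety population is the reader's own; the protocol does not make it.

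Replacing the sentence with an expected total of 28 to 37 would not improve it. That range is a forecast the protocol does not make, and it leaves out several of the routes listed in the working.

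**Conclusion.** The concern does not call for a change. What remains is an unnamed definition in two sentences. Table 1 shows openly that 25 patients had entered by Cohort 6 and that more cohorts were to come, and a reader can add the rest from Tables 1 and 3.

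On the safety reading the excess over 25 is 3 patients with the smallest full intra-patient plan, arguably still about 25, and 12 with the flat plan. This assumes that all 25 received some drug and that there are no further expansions, repeats or replacements. On the dose-review reading there may be no excess at all; the protocol does not settle it. In either case the size is approximate, conditional on escalation and not based on power, and no decision rule or analysis takes it as an input. Naming the definition would be harmless, but it would alter neither the conduct of the trial nor its conclusions.
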